6.13 Analysis of Exploratory Endpoints

6.13.1 Change in CCI [REDACTED]

Change from baseline in the CCI [REDACTED]

CCI [REDACTED]

CCI This analysis method is similar to the analysis for the second co-primary endpoint (Section 6.11.2).

6.13.2 Change in CCI

Change from baseline in CCI summary (including domain scores) will be analyzed using CCI
similar to Section 6.12.5.

6.13.3 Subjects Achieving CCI at Week 24

For subjects with CCI at baseline, the proportion of subjects achieving CCI at Week 24 will be analyzed using the CCI similar to Section 6.11.1.

6.13.4 Change in CCI

Change from baseline in CCI similar to Section 6.12.5 with CCI
similar to Section 6.12.5 with CCI

6.13.5 CCI

Change from baseline in CCI as described in Section 6.12.5. The model will include CCI
similar to Section 6.12.5 with CCI

- CCI
- CCI
- CCI
- CCI
- CCI
- CCI

- CCI [REDACTED]
[REDACTED]
[REDACTED]
[REDACTED]
- CCI [REDACTED]
[REDACTED]
[REDACTED]
[REDACTED]

6.13.6 CCI [REDACTED]

Methods for CCI [REDACTED] and CCI [REDACTED] are described in a separate analysis plan.

6.14 Analysis of Pharmacokinetic Endpoint

The analysis of the PK concentration will be based on the Safety population. AK002 concentrations will be listed by treatment, subject, nominal time, and actual time. Concentrations that are below limit of quantification (BLOQ) will be indicated in the listing.

Plasma concentrations will be summarized at each nominal time point separately for each treatment. The following descriptive statistics will be presented: n, arithmetic mean, SD, geometric mean, % CV, median, minimum, and maximum.

Individual plasma concentration vs. actual times will be plotted for each subject in linear and semi-logarithmic scales, placed on the same page. Mean plasma concentration at the scheduled time points will be plotted for each treatment in linear and semi-logarithmic scale, with the associated standard errors (for linear scale only) at each scheduled time point.

In the plot, concentrations that are BLOQ will be assigned a value of 0 if they are collected predose or assigned a value of 1/2 the lower limit of quantification (LLOQ) if they are collected postdose.

Analysis of PK parameters are specified separately in a PK analysis plan.

6.15 Safety Analyses

6.15.1 Adverse Events

Safety assessments will be based mainly on the nature, frequency, relationship, and severity of adverse events (AE). The AE will be coded by primary SOC and PT according to MedDRA (version 21.0). The treatment-emergent adverse events (TEAE) will be summarized by the number and percentage (n and %) of subjects in each SOC and PT.

For summaries by relationship to study drug, “possibly related” will be combined with “related”, and “unlikely/remotely related” will be combined with “not related.” When multiple AE are reported with the same PT, the AE of the strongest relation to study drug will be included in the summary by relationship, and the AE of the most severe grade will be included in the summary by severity table.

The following AE incidence tables will be presented.

- Overview of TEAE to include
 - Number (%) of subjects who reported at least 1 TEAE
 - Number (%) of subjects who reported at least 1 treatment-related TEAE
 - Number (%) of subjects who reported at least 1 severe TEAE
 - Number (%) of subjects who reported at least 1 serious TEAE
 - Number (%) of subjects who reported at least 1 TEAE leading to treatment discontinuation
 - Number (%) of subjects who reported at least 1 TEAE leading to study discontinuation
 - Number (%) of subjects who reported at least 1 TEAE of special interest (TEAESI)
- TEAE by PT sorted by decreasing order of subject incidence in the combined treatment group
- TEAE by SOC and PT in alphabetical order
- TEAE by SOC, PT, and maximum severity
- TEAE by SOC, PT, and strongest relationship to study drug
- TEAE leading to treatment discontinuation by SOC and PT, if warranted by sample size
- TEAE leading to study discontinuation by SOC and PT, if warranted by sample size
- Serious TEAE by SOC and PT, if warranted by sample size
- TEAESI by SOC and PT

All AE will be listed with onset/stop day, relationship to study drug, severity, action taken, and outcome. Pertinent subject information including treatment group and demographics will also be included.

Separate listings will be provided for TEAE leading to study discontinuation, TEAE of special interest, and treatment-emergent serious AE (TESAE).

6.15.2 Laboratory Test

Laboratory data will be summarized by presenting summary statistics of raw data and change from baseline values (means, medians, standard deviations, ranges). For quantitative laboratory parameters, both actual values and change from baseline values will be summarized at each visit.

Shift tables will be presented, in which, lab test results at baseline and post-baseline visit will be classified into below ($<\text{LLN}$), within ($\geq\text{LLN}$ and $\leq\text{ULN}$), and above ($>\text{ULN}$) normal ranges.

Subject incidences (n and %) will be presented for the shift from baseline to the post-baseline visits.

Note that the analysis window will be applied for the visits.

A complete laboratory data listing, including hematology, biochemistry, and urinalysis will be provided for all subjects.

6.15.3 Vital Signs, Height and Weight, and Other Safety Measures

Vital signs will be summarized by presenting summary statistics of raw data and change from baseline values (means, medians, standard deviations, ranges) for each visit (per analysis window) and time point. A data listing will include vital signs from all visits.

6.15.4 Electrocardiogram

Incidence of the Investigator's overall assessment (normal, abnormal – not clinically significant, and abnormal – clinically significant) will be summarized.

6.15.5 Physical Examination

New or worsening symptoms in the symptom-directed physical exams will be included in the by-subject data listing.

6.15.6 Analysis of Anti-Drug Antibody

A data listing of anti-drug-antibodies (ADA) results will be provided for all subjects. Number (%) of subjects who are confirmed ADA-positive at any time after receiving study drug and number (%) of subjects who are confirmed ADA-positive at the end of study will be cross-tabulated by their ADA status and titers at predose.

7. Validation

The Clinical Operations and Data Management at Allakos will work with the EDC/Data Management (DM) vendor to ensure that the data collected for the study are of the highest quality possible. The study monitor will be responsible for reviewing and verifying the accuracy

of the data recorded on the eCRF directly from source documents at the investigative site. The DM vendor will be responsible for performing edit checks and reviewing all data entered into the electronic database to identify discrepant and/or inconsistent values and to send queries to the clinical sites. The Investigator will be responsible for answering queries about discrepant data and providing electronic signatures to confirm data integrity.

The programming of tables, listings and figures (TLF) based on the clinical data is outsourced. Allakos seeks to ensure the quality of the reports provided by the CRO in the form of TLF passing a rigorous validation process as follows:

- Derived datasets will be independently reprogrammed by a second programmer. The separate datasets produced by the 2 programmers must match 100%.
- Tables will be independently reprogrammed by a second programmer, and the results from both programs must match.
- Figures will be checked for consistency against corresponding tables and listings or independently reprogrammed if there are no corresponding tables or listings.
- Listings will be checked for consistency against corresponding tables, figures, and derived datasets.

All post hoc analysis, if accepted for inclusion in the study report, will follow the same quality process as stated above. The entire set of TLF will be checked for completeness and consistency prior to delivery to Allakos.

8. References

International Council for Harmonisation (ICH). Guideline for industry E3, structure and content of clinical study reports, July 1996.

Food and Drug Administration. E9 (R1) Statistical Principles for clinical trials: addendum: estimands and sensitivity analysis in clinical trials. Guidance for industry, ICH, May 2021.

9. Appendices

9.1 Appendix 1: Effect of Missing Data on the Weekly Mean of TSS

Following the FDA's suggestion for the evaluation of the missing daily diary effect on the weekly mean of TSS score, data from the Phase 2 study are extracted. The Phase 2 study has diaries collected daily over 14 weeks of the treatment period. A simulation study was conducted examining the changes in standard error by the number of missing daily diaries that were randomly created. The steps are as follows.

- 1) A complete data set is created in which a subject week is kept only if the week has all 7 daily diaries. This data set is at the subject-day level.
- 2) For each week in the complete data set, 1 of the 7 daily diaries is randomly set to missing. This creates a data set with 1 day per week missing.
- 3) Step 2 is repeated for 2 of the 7 daily diaries are randomly set to missing to create a data set with 2 days per week missing.

Finally, a data set is created with 6 days per week are randomly set to missing.

- 4) For each of the 7 data sets (0 day/week missing, 1 day/week missing, ..., 6 days/week missing), daily diaries are averaged to derive the weekly mean for each subject at each week.
- 5) Weekly means of the diaries are further averaged across all subjects to derive the population means and population standard error of the diaries for each week.
- 6) Steps 2 through 5 are repeated 500 times. Each time, the daily diaries are randomly set to missing.
- 7) The 500 weekly population standard errors from Step 6 are averaged and presented in the table below.

As expected, the standard error increases as the number of missing daily diaries increases, indicating the estimate of weekly TSS mean becomes less accurate. However, the increase in the standard error does not exceed 2% when allowing 3 out of 7 daily diaries missing, and does not exceed 4% when allowing 4 out of 7 daily diaries missing.

Table 7 Standard Errors for the Mean Weekly TSS Diaries by Number of Daily Diaries Missing Averaged over 500 Simulations

Week	Number of Daily Diaries Missing						
	0 Day	1 Day	2 Days	3 Days	4 Days	5 Days	6 Days
1	3.092	3.100	3.115	3.132	3.166	3.232	3.405
2	2.917	2.923	2.929	2.941	2.964	3.003	3.102
3	3.070	3.081	3.088	3.095	3.125	3.198	3.321
4	2.862	2.868	2.874	2.881	2.894	2.926	2.994
5	3.111	3.118	3.122	3.134	3.149	3.187	3.293
6	3.135	3.137	3.147	3.154	3.170	3.191	3.279
7	3.039	3.045	3.054	3.067	3.093	3.140	3.283
8	3.842	3.846	3.849	3.858	3.871	3.884	3.959
9	2.854	2.869	2.874	2.899	2.932	3.021	3.176
10	2.823	2.829	2.840	2.845	2.857	2.886	3.010
11	2.997	3.002	3.010	3.008	3.037	3.069	3.148
12	2.656	2.661	2.671	2.689	2.691	2.731	2.842
13	2.864	2.879	2.886	2.905	2.950	3.011	3.208
14	2.388	2.402	2.414	2.437	2.474	2.580	2.795

Source: K:\AK002-016\planning\MissingOnSE.sas 08MAR2020

9.2 Appendix 2: Intercurrent Events

A. Use of any of the following prohibited medications during the course of the study as described

- 1) Immunosuppressive or immunomodulatory drugs (e.g., IL-5 modulators, i.e., benralizumab, reslizumab, mepolizumab; IL-4 and IL-13 antagonists, i.e., dupilumab; calcineurin inhibitors, i.e., cyclosporin, tacrolimus; mTOR inhibitors, i.e., sirolimus, everolimus; anti-metabolites, i.e., azathioprine, methotrexate, 6-mercaptopurine, leflunomide, mycophenolate mofetil; alkylating agents, i.e., cyclophosphamide; TNF inhibitors, i.e., infliximab, adalimumab; anti-IgE antibodies, i.e., omalizumab; and eosinophil-depleting drugs, i.e., pramipexole.
 - a) Use at any point during the study.
- 2) Glucocorticoids
 - a) Initiation of any course of treatment or single use of systemic or swallowed corticosteroids at a dose of >10 mg/day prednisone or equivalent starting at Week 21 and through the end of Week 24. This does not include use of corticosteroids given as pre-infusion prophylaxis or treatment of IRR.

B. Use of restricted medications outside the protocol-defined specifications

- 1) Glucocorticoids
 - a) Discontinuation of a previously stable dose of systemic or swallowed corticosteroids (≤ 10 mg/day prednisone or equivalent) after the screening period.
 - b) Initiation of a new course of systemic or swallowed corticosteroids (≤ 10 mg/day prednisone or equivalent) following the screening period and continuing to at least study Week 21 (within 2 weeks of efficacy assessment at Weeks 23 and 24).
- 2) Proton Pump Inhibitors
 - a) Discontinuation of a previously stable dose of an oral PPI after the screening period and before the end of Week 24.
 - b) Initiation or increase in the dose of an oral PPI following the screening period and continuing to at least study Week 21 (within 2 weeks of efficacy assessment at Weeks 23 and 24).
- 3) Sodium cromolyn
 - a) Discontinuation of a previously stable dose of sodium cromolyn after the screening period and before the end of Week 24

- b) Initiation or increase in the dose of sodium cromolyn following the screening period and continuing to at least study Week 22 (within 1 week of efficacy assessment at Weeks 23 and 24).

C. Discontinuation of Investigational Medical Product

- 1) Discontinuation of study agent due to:
 - a) Infusion-related reaction
 - b) Subject withdrawal
 - c) Meeting study withdrawal criteria (Protocol Section 13.10)

Per protocol, subjects are required to remain on stable doses of either PPI or corticosteroids (≤ 10 mg prednisone equivalent per day) throughout the course of the study if they are on a stable dose during the screening period. Because of the potential impact of corticosteroids and PPI on both histologic assessment of tissue eosinophil levels as well as subject reported GI symptoms, subjects must meet the entry requirements for both histology and symptom burden (TSS6) if they are on any of these medications at screening and therefore must remain on a stable dose throughout the study in order to meaningfully interpret any change from baseline during the evaluation phase. Conversely, subjects starting these medications due to unforeseen medical necessity following the screening period and remaining on them through a time point sufficiently close to the evaluation period to potentially impact assessment of symptoms and/or histologic assessments will be considered as intercurrent events. For PPI and corticosteroids (≤ 10 mg/day prednisone or equivalent) a conservative washout period is estimated at 2 weeks, and therefore, continuation of a new course of therapy beyond Week 21 could be considered as a potential ICE.

Sodium cromolyn is a mast cell stabilizer and could potentially impact reported symptoms in a similar way to 1 of the mechanisms of action of AK002. As such, discontinuation of a previously stable dose of sodium cromolyn after the screening period and before the end of Week 24 could be considered as a potential ICE. Likewise, the initiation or increase in the dose of sodium cromolyn following the screening period and continuing to at least study Week 22 (within 1 week of efficacy assessment at Weeks 23 and 24) could be considered as a potential ICE. It is estimated that 1 week would be a sufficient washout period for the effects of sodium cromolyn.

Antihistamines are unlikely to impact histologic assessments in the study but could have slight impact in some symptoms depending on the type, dose, and duration of use. As such, subjects are required to stay on stable doses of antihistamines if they are taking them at the time of screening and to remain on them through completion of the study. Due to unforeseen medical circumstances and acknowledging that some subjects may have concurrent allergic conditions, the use of these medications by some subjects during the study is anticipated.

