4.2.4 Intercurrent Events

The events below are considered intercurrent events (ICE) confounding with the efficacy outcomes.

- Premature discontinuation from the study
- Use of prohibited/restricted medication

Further clarification and handling of ICE including prohibited/rescue medications is detailed in [Appendix 2](#).

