4.2.5 Strategy for Handling Intercurrent Events

For the analysis of the study product estimand, tissue eosinophil values and TSS will be counted as non-responders for binary variables and set to missing for continuous outcomes from the point when an ICE occurs. An appropriate method for handling missing data through statistical modeling (e.g., multiple imputation [MI]) will be used (Sections [5.4.1](#), [5.4.2](#), and [6.11](#)). The estimand will provide an answer to the question that is crucial to individual subjects:

“If I take this study drug as part of my treatment regimen, without adding any further medications that may impact the underlying disease or exit the study prematurely, what improvements in histology and PRO symptoms might be anticipated after 24 weeks?”

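### SAP Appendix 2 does not list as an intercurrent event a corticosteroid course above 10 mg/day begun before Week 21 and still running at Weeks 23–24, although it lists the same course at or below 10 mg/day

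*SAP*

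**What the plan says.** SAP section 4.2.4 names "Use of prohibited/restricted medication" as an intercurrent event and leaves the detail to Appendix 2 (section 9.2). Three parts of that appendix bear on corticosteroids.

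- **Item A.2.a (above 10 mg/day).** It stands under the heading "Use of any of the following prohibited medications during the course of the study as described". The trigger is initiation of a course, or a single use, of "corticosteroids at a dose of >10 mg/day prednisone or equivalent starting at Week 21 and through the end of Week 24". Pre-infusion prophylaxis and treatment of infusion-related reactions (IRR) are excepted.
- **Item B.1.b (at or below 10 mg/day).** The trigger is a new course "mg/day prednisone or equivalent) following the screening period and continuing to at least study Week 21".
- **Narrative after the list.** ICE status is given to "subjects starting these medications due to unforeseen medical necessity following the screening period and remaining on them through a time point sufficiently close", meaning near the time when efficacy is assessed. A later sentence, limited to PPIs and to corticosteroids at or below 10 mg/day, gives a 2-week washout and says "continuation of a new course of therapy beyond Week 21 could be considered as a potential ICE".

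The consequences are in SAP sections 5.4.1 and 5.4.2. Daily symptom scores after an ICE are set to missing, and a missing Weeks 23–24 TSS is multiply imputed. A tissue count after an ICE is set to missing, then replaced by an earlier unscheduled post-baseline count or, if there is none, counted as failure.

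Protocol 8.1 prohibits use above 10 mg/day, with exceptions. Protocol 8.2 permits it for a medically necessary unrelated condition, so a long course can arise without a protocol violation.

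**The concern.** ICE status decides whether a patient's outcome is used as observed in both co-primary analyses. The estimand in SAP 4.2.5 asks what happens "without adding any further medications that may impact the underlying disease". Appendix 2 itself explains that corticosteroids can affect both histology and reported symptoms. On a literal reading, a patient taking more than 10 mg/day throughout Weeks 23–24 keeps observed values if the course began before Week 21, while a patient on a lower dose over the same dates does not. That conflicts with both the estimand and the appendix's own reasoning.

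The planned checks do not close the gap. The two missing-not-at-random analyses (SAP 6.11.5) reset only data on or after an ICE, so they inherit the classification. The per-protocol analysis removes major violations, and a course permitted under Protocol 8.2 may not be one.

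A smaller point in the same place: the PPI item covers "Initiation or increase in the dose of an oral PPI following the screening period", and the cromolyn item has the same form, but B.1.b says nothing about dose increases.

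**Working it through.** **1. Calendar.** Study weeks are 7-day blocks from Day 1 (SAP Table 2). Week 21 starts on Day 20 × 7 + 1 = 141. Weeks 23–24 run from Day 22 × 7 + 1 = 155 to Day 24 × 7 = 168. Since 155 − 14 = 141, A.2.a's window already opens two weeks before Week 23.

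**2. The two rules applied to the same courses.** A.2.a is taken as start week 21 to 24. B.1.b is taken as start after screening and last week 21 or later.

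| Course (weeks) | Above 10 mg/day: A.2.a | At or below 10 mg/day: B.1.b |
|---|---|---|
| 10–12 | not an ICE | not an ICE |
| 10–20 | not an ICE | not an ICE |
| 18–24 | **not an ICE** | **ICE** |
| 20–24 | **not an ICE** | **ICE** |
| 20–21 | **not an ICE** | **ICE** |
| 21–24 | ICE | ICE |
| 23–24 | ICE | ICE |

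For continuing courses the rules differ exactly when the course begins before Day 141 and continues into Week 21 or later. Within Weeks 21–24, A.2.a is the stricter rule, because a single use counts. No other item fills the gap: B.1.a is also limited to 10 mg/day or less, and section C concerns only discontinuation of study drug.

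**3. The plan's own power.** Inputs from SAP 3.5: n = 80 per arm, difference 7.4, SD 12.5, two-sided 0.05. The standard error is 12.5 × √(2/80) = 1.976, so the noncentrality is 7.4/1.976 = 3.74 on 158 degrees of freedom. Power is 96.1%, which reproduces the stated 96%.

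**4. Possible size for TSS.** Patient counts and gains are assumptions; the documents give neither. If k more patients are affected in one arm than in the other, each with a steroid gain of g points, the mean difference moves by k × g/80. With g = 7.4 that is 0.0925 per patient.

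| Net excess in placebo | Difference | Power |
|---|---|---|
| 0 | 7.400 | 96.1% |
| 2 | 7.215 | 95.2% |
| 4 | 7.030 | 94.2% |
| 8 | 6.660 | 91.8% |
| 10 | 6.475 | 90.3% |
| 11 | 6.383 | 89.4% |

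Power reaches 90% at a difference of 6.446, that is (7.4 − 6.446)/0.0925 = 10.3 patients. With half the gain (3.7), 8 net patients shift the difference by 8 × 3.7/80 = 0.37 and leave 94.2%.

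For the opposite direction, take no true TSS effect, a net excess in AK002 and g = 7.4. The chance of a TSS result significantly favouring AK002 rises from 2.5% to 3.1% (2 patients), 3.8% (4) or 5.6% (8). This is the TSS test alone; trial success also needs the tissue endpoint.

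**5. Tissue endpoint.** Exact power of Fisher's test at 0.60 versus 0.10 with 80 per arm exceeds 99.99%. Suppose 10% of placebo patients were treated and all became responders: the placebo rate would be 0.10 + 0.10 × 0.90 = 0.19, and power would be 99.97%.

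**The case against.** The strongest reply is that the appendix already covers the case.

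- **Narrative.** The sentence just before its general rule speaks of corticosteroids and PPIs with no dose limit. The rule's reference to medical necessity echoes the protocol's exception for higher doses, and its consequence is stated firmly. The softer wording belongs to the later sentence about lower doses.
- **List.** Heading A speaks of use, and A.2.a includes single use, so every dose taken in Weeks 21–24 might count. The literal reading makes one dose on Day 141 an ICE but daily dosing on Days 140–168 not, which is unlikely to be intended.
- **Body text.** Prohibited use outside the exceptions falls under the general category in SAP 4.2.4 anyway.
- **Checks.** All ICEs are listed (SAP 6.11), and independently programmed datasets must agree completely (SAP 7), so a mismatch would surface.
- **Size.** Every patient count is assumed.

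Much of this stands. The intent was probably to include these courses, and the open case is narrow: mainly a permitted course for an unrelated condition, begun before Day 141 and still running. But A.2.a says *initiation* and lacks the continuation clause that B.1.b has. The narrative puts the 10 mg limit on corticosteroids both before and after its general rule. Double programming would expose a disagreement without supplying the prespecified answer. The size argument limits the importance of the point; it does not reconcile the texts.

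**Conclusion.** The concern holds. The listed items of Appendix 2 treat a higher-dose course begun before Week 21 more leniently than the same course at a lower dose, and the surrounding text does not settle which reading governs. Two programmers could classify the same patient differently, with consequences for both co-primary endpoints.

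This is an ambiguous rule, not a demonstrated bias. Frequency, direction and size are unknown, equal use with equal gain in both arms cancels, and nothing in the documents suggests imbalance. Under the assumed gain of 7.4 points, a net placebo excess of 11 patients is needed before TSS power falls below 90%, and the tissue endpoint's power is insensitive. It should be fixed because the rule conflicts with the plan's own estimand and the correction is cheap. The silence of B.1.b on dose increases is a lesser omission, and the conclusion does not depend on it.

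**What to change.** Amend SAP Appendix 2 before unblinding, for analysis classification only:

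1. In A.2.a, state that a course above 10 mg/day started after screening and still ongoing in that item's Week 21–24 window is an ICE whatever its start date. Keep the existing exceptions for premedication and treatment of IRR.
2. Make the narrative agree with A.2.a and B.1.b, and say plainly that its general rule applies above 10 mg/day as well.
3. In B.1.b, state how dose increases are classed, in line with the PPI and cromolyn items.

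Permitted treatment does not change. No protocol amendment is needed, because the SAP supersedes the protocol's statistical methods (SAP section 1; Protocol section 15). The cost is a few lines of text. No new data are required, since concomitant medication is already recorded with dose and dates (Protocol 11.3.1). The downside is possibly a few more ICE classifications, with more imputed TSS values and tissue counts set to missing.
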